Participants might trip and fall while walking which could result in musculoskeletal injury such as an ankle sprain. To minimize this risk, participants will wear a harness that will prevent them

from falling more than several inches if they were to trip or stumble during walking. Participants will also be given time to accommodate to walking on a treadmill. The treadmill and Agility Trainer both have emergency shut-off “kill” switches to rapidly disengage the devices at any time. The emergency shut down switches will be easily accessible to both the physical therapist and the participant.

Discomfort due to Forces applied to the Pelvic Harness

We will use a padded hip belt and offer all participants additional padding as desired to minimize any discomfort. In addition, the Agility Trainer has a number of safety features that limit the magnitude of force that can be applied to participants, including mechanical stops to ensure the device does not move participants beyond their normal range of motion and emergency shut off switches that will be within reach of both participants and researchers during testing. Also, we will very gradually increase the magnitude of force the device applies to participants and continually monitor participants’ responses so that the magnitude of the applied forces does not exceed the individual’s ability. Finally, the pelvic harness (Barry USA Inc., Delaware) is well padded and was designed to comfortably suspend circus trapeze performers.

Emotional Discomfort

Some of the questions we ask may be upsetting, or participants may feel uncomfortable answering them. If they do not wish to answer a question, they may skip it and go to the next question.

Availability of Emergency Services

All assessments and training sessions will be conducted at the Northwestern University Feinberg School of Medicine. In the event of an emergency, this facility is equipped to provide immediate care to participants. In addition, a physical therapist will be present during all experimental and training sessions. The physical therapist will continually monitor the cardiopulmonary condition of the participant and attend to any immediate health-related issues.

Potential Benefit of the Proposed Research to the Participant and Others

The overarching goal of this project is to assess the effects of a novel intervention, *locomotor training performed in a movement amplification environment*, on dynamic balance and participation in walking-related activities in individuals with iSCI. Recent scientific research [64, 65] has provided an evidence-based framework for motivating the development of tools able to create the movement amplification training environment examined in the proposed research. Locomotor training performed on a treadmill is frequently administered in clinical settings and is well-accepted because it provides a safe and straightforward method of intensely training many of the important components of walking while not requiring much space or complex equipment. However, treadmill training alone is limited because it lacks a balance-specific component. If outcomes from the proposed research are successful, the supplementation of treadmill-based locomotor training with a movement amplification environment could dramatically improve the capacity of treadmill training to enhance dynamic balance. The movement amplification

environment has the potential to transform an ordinary treadmill into a dynamic environment where people with iSCI can receive safe, challenging, and customized locomotor balance training. Overall, this proposal has the potential to dramatically enhance how gait rehabilitation is delivered and, most importantly for Veterans recovering from iSCI, the intervention may provide a means to significantly improve components of their walking effected by balance.

Several clinical gait rehabilitation breakthroughs have often been spawned from research originally developed for individuals with SCI (e.g. body weight supported treadmill training [98], robotic assisted gait training [99]). Similarly, we believe the tools and training procedures developed within the current proposal have broad applications that extend far beyond those recovering from SCI. The approach we are using has the potential to benefit a wide range of impaired populations that experience balance-related deficits (i.e. stroke, TBI, lower-limb amputee, older adults). The development of tools to enhance dynamic balance may also benefit non-impaired populations in specific professions that require excellent balance such as war fighters, search and rescue teams, and athletes. Thus, outcomes from the proposed research may provide the ground work to develop dynamic-balance related interventions for a broad range of applications.

All participants in the proposed study will receive high intensity locomotor training under the supervision of an experienced clinician. The benefits of exercise in the iSCI population can improve physical and emotional well-being [100]. In addition, there is strong evidence that locomotor training can improve walking speed, and endurance [3, 60, 101]. This intervention will also target the enhancement of dynamic balance during walking. As such, individuals enrolled in the proposed study may improve aspects of their health and functional walking ability. However, as this is an experimental study, it possible that participants may not improve their own walking ability by participating. The risks of participating are similar to that involved when participating in any physical therapy intervention aimed at improving gait.

Importance of the Knowledge to be gained

For people with SCI, balance deficits negatively impact elements of walking critical for participation in mobility-related activities. We hypothesize that for individuals with iSCI locomotor training performed in a movement amplification environment will substantially improve dynamic balance and participation in walking activates. Currently, many clinically-accepted gait rehabilitation practices including body weight supported treadmill training are likely sub-optimal for teaching locomotor balance because they lack effective balance-specific training components. Presently, there is an absence of evidence-based clinical tools to address this shortcoming. Outcomes from this project will enhance our understanding of how individuals with iSCI learn dynamic balance. This study will investigate a motor learning paradigm – amplification of an individual's own movements – that has shown promise for teaching control of upper extremity movements of individuals with neurologic injury [64, 65]. This project will extend this paradigm to train dynamic balance during walking. If successful outcomes from this study will provide a foundation for development of new technologies that can be used to apply movement amplification type environments to current gait rehabilitation practices used within the VA clinical setting.

In addition, our general understanding of how locomotor training interventions impact participation in walking-related activities of individuals with iSCI is poor [96]. This study will provide quantitative measures on how locomotor training, and locomotor training that includes a targeted dynamic balance component influence participation in walking activities. Frequently reported clinical outcome measures, such as 10-meter walk speed or 6-minute walk distance are valuable for understanding an individual's function, but these measures taken in a laboratory or clinic setting are not sufficient to gage participation. As technology to assess participation using simple wearable devices has advanced, it is important that researchers include measures of participation when evaluating locomotor training interventions. Research suggests that dynamic balance is a primary determinate of walking activity in individuals with iSCI. Currently it is unknown if engagement in training interventions targeting balance will be effective for improving participation in walking activities. Outcomes from this study will fill this void in our knowledge and provide data that will be essential for developing normative standards for changes in walking participation following locomotor training interventions.

- **Provide description of the study population (delineate all categories of subjects – patients, providers, family members, employees, etc.). Include anticipated enrollment numbers**

We aim to enroll 46 Veterans and non-Veterans with chronic motor incomplete SCI who are ambulatory. We will include participants with a range of initial functional walking abilities evaluated by walking speed (half the participants' walking speed will be < 0.5 m/s at the start of the study). All potential study participants will be screened to ensure they meet the study inclusion/exclusion criteria.

Participation in this study is open to all individuals who meet the inclusion exclusion criteria for participation. Participation will be open to people of all racial and ethnic backgrounds, gender, and sexual orientation. Minorities and female participants will be actively recruited and their representation in the study is anticipated to match population demographics. Specifically, we anticipate that the ethnic and racial diversity of our participants will match the composition of the greater Chicago metropolitan area. In 2010 the United States Census Bureau reported the population of Chicago had the following ethnic and racial composition:

- Hispanic or Latino (of any race) 29%
- Not Hispanic or Latino 71%
- American Indian and Alaska Native 0.5%
- Asian 5%
- Native Hawaiian and Other Pacific Islander 0.0%
- Black or African American 33%
- White 45%

By gender, 80% of individuals with SCI are male. As such we anticipate that the male to female ratio of participants in this study will be 80% male and 20% female. This study will not include individuals under 18 years of age or vulnerable populations. Women of childbearing potential will not be excluded, although women who are pregnant will be excluded because of pregnancy-related body changes on balance.

- **Include rationale for including or excluding certain populations – in particular vulnerable populations.**

Participation in this study is open to all individuals who meet the inclusion exclusion criteria for participation.

- **As applicable, provide information on any added protections for vulnerable populations.**

This study will not recruit or enroll vulnerable populations.

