We will conduct all locomotor training interventions in the Human Agility Laboratory. All training will be directed by a licensed physical therapist. Training for each intervention group will be conducted on a large commercial treadmill - belt width 1.39 m (Tuff Tread, Willis, TX) providing space to perform side steps and small lateral maneuvers [82]. For safety, participants will wear a trunk harness attached to a passive overhead safety support. Support straps will be adjusted to allow unrestricted travel across the treadmill and will not provide bodyweight support. During locomotor training, participants will wear a heart-rate monitor, to provide continuous feedback to the physical therapist on the intensity of the training, and an activity monitor, to measure number of steps during the session. For the Experimental group, the training equipment will also include the Agility Trainer to produce the movement amplification environment.

The locomotor training intervention will include 20 sessions (2 to 3 times per week). Each training session will last up to 60-minutes. The objective each session is for the participant to complete a total of 45-minutes of treadmill walking. The additional time each session will be used as needed for setup and rest breaks.

Control group: Participants randomized to the Control group will complete high intensity gait training on a treadmill. The protocol is based on evidence demonstrating that for individuals with iSCI high intensity training based on heart rate (HR) and perceived exertion (RPE) [83] resulted in significantly greater increases in treadmill and over ground walking speeds than lower intensity training interventions [60]. The goal of each session will be to achieve 40-minutes of stepping practice within a desired range for HR and RPE. We will continuously adjust training parameters to maintain a target HR between 70 and 80% of estimated age-predicted HR reserve. We will calculate HR reserve as follows:

$$\text{HR reserve} = (\text{HR maximum} - \text{HR resting}) + \text{HR resting}$$

We will estimate HR maximum [84] as: $\text{HR maximum} = (208 - (0.7 \times \text{age}))$. If target heart rate zones cannot be achieved during training, we will use RPE as a secondary measure of intensity. We will target a rating of 15 "hard" to 17 "very hard" on the 20-point RPE rating scale during training.

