Every training session will begin and end with a 2.5-minute warmup and cool down respectively. During these periods, individuals will perform straight treadmill walking. Target heart rate during these periods will be between 50 and 65% of HR reserve. The 40-minute body of the training session will be divided into four 10-minute segments. Two of the 10-minute segments will consist of **Speed-training**. The objective during Speed-training will be to achieve the highest possible speed during straight-forward treadmill walking while maintaining the target HR and RPE. The other two 10-minute segments will consist of **Balance-training**. The objective during the Balance-training segments will be to maximize repetitions of forward treadmill walking while introducing additional challenges to dynamic balance. We will utilize the following tasks to challenge dynamic balance:

- 1) *Lateral Stepping Maneuvers.* We will draw a chalk line down the center of the treadmill. During forward walking the physical therapist will cue the participant to move from one side of the chalk line to the other. Task difficulty will be increased by increasing the frequency of lateral maneuvers performed.
- 2) *Head Turns.* Participants will perform cued vertical and horizontal head turns while maintaining forward walking. Task difficulty will be progressed by increasing the magnitude and duration of the head turns.
- 3) *Obstacle negotiation.* Participants will be tasked with stepping over small objects during forward walking. Task difficulty will be progressed by increasing the size and frequency of obstacles.

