Within the clinical decision-making framework (described below) combinations of the balance challenging tasks will be selected to; avoid repeated failures (loss of balance requiring physical assist from physical therapist to recover), achieve the appropriate heart rate and RPE, and consider the participant's tolerance/needs. At the physical therapist's discretion participants will be provided with hand-held assist as necessary to safely-perform the desired stepping tasks. Our goal will be to minimize any external support provided to the participants. Seated or standing rest breaks will be permitted as needed. Brief rest breaks will naturally occur during transitions between segments. We will monitor the individual and cumulative rest break time each session. We will set goals to decrease the individual and cumulative duration of rest breaks over the course of the training intervention.

The order of the individual 10-minute Speed- and Balance-training segments will be alternated within a session. We will alter which segment type (Speed- or Balance-training) is presented first from session-to-session.

Experimental group: The locomotor training protocol described for the Control group will be used for the Experimental group with one exception. The Experimental group will perform all

Speed- and Balance-training within the movement amplification environment. The objective for the Experimental group will be to progressively increase the movement amplification gain within and across sessions to increase the challenge for the participant to control their lateral COM motion. The gain of the movement amplification environment will be initially set very low (25 Nms^{-1}). When a participant can successfully ambulate in the low intensity movement amplification field without repeated failures (loss of balance requiring physical assist from physical therapist to recover), we will incrementally increase the gain of the field by (5 Nms^{-1}). We will continue to increase the gain until we reach a maximum gain of 55 Nms^{-1} dictated by the current Agility Trainer hardware and software.

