Clinical Decision-Making: To ensure consistency of the intervention between participants, a simple clinical decision-making protocol will be used to guide the physical therapist's decisions about when to change intervention parameters. First the physical therapist will determine: is the participant able to accomplish the immediate walking task? Second, the physical therapist will determine: is HR and RPE in the target zone?

Is the participant able to accomplish the immediate walking task?

The immediate walking task during Speed-training is straight-forward walking. The task during Balance-training is straight-forward walking + an additional balance challenge. The physical therapist will determine that the participant is able to successfully accomplish the task if; *the participant is able to make positive reciprocal steps without limb collapse or loss of balance requiring assistance for 1-minute of walking.*

- **If successful.** First reduced or eliminate any handheld assistance. Next, if applicable, increase movement amplification gain by 5 Nms^{-1} (up to 10 Nms^{-1} above the participant's previous highest gain within a single session or a maximum of 55 Nms^{-1}). Finally, if applicable, increase the challenge of the balance-training task. Reevaluate every minute.
- **If unsuccessful.** First, if applicable, decrease the challenge of the balance-training task. Next, if applicable, decrease the movement amplification gain by 5 Nms^{-1} (to a minimum of 25 Nms^{-1}). Finally, provide handheld assist as needed to perform the task successfully. Reevaluate every minute.

Is HR and RPE in the target zone?

Once the participant is able to successfully accomplish the walking task then the treadmill speed should be adjusted to achieve the desired HR and RPE.

- **If HR and RPE are below the target zone.** Increase treadmill speed by 0.1-0.3 mph. Reevaluated every 30 seconds.
- **If HR and RPE are above the target zone.** Decrease treadmill speed by 0.1-0.3 mph (treadmill speed should not go below the speed used during the session's warmup period). Reevaluated every 30 seconds. If HR and RPE remain above the target zone upper limit, then give a rest break.

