We recognize that there is an interaction between the two decision-making trees. Specifically, increasing balance-challenges may increase the cardiovascular demands of walking, and increasing walking speed may increase the challenge to maintain dynamic balance. Based on our goal to provide targeted dynamic balance training, we will prioritize successful accomplishment of the task and stress progression of the dynamic balance demands (elimination of any handheld assist, progression of movement amplification gains, and progression of the balance-challenging tasks). We realize that for lower functioning participants prioritizing the balance challenging components of walking may result in HR and RPE below the target threshold. However, our pilot testing found that we were able to consistently adjust the movement

amplification gains, balance-challenging tasks, and walking speeds in a manner that consistently placed individuals in the target HR and RPE zone.

Documentation of Intervention

A research assistant will be present at every session to assist the physical therapist and document the following events at every training session. Specifically, we will record:

Vital signs before, during, and after training;

Total time walking within the 60-minute session;

Total number of steps (StepWatch, Modus, Washington DC);

Walking speeds:

Number of times **physical assistance** (from the physical therapist or overhead safety support) was provided to prevent fall (fall defined as inability to recover loss of balance without physical assistance);

Specific balance-challenging tasks practiced each session;

Movement Amplification environment gains (if applicable); and

Exertion and workload - monitored via heart rate and the 6-20 RPE scale throughout the session.

Assessment of Locomotor Training Effects

Clinical Outcome Measures

We will collect clinical outcome measures at four time points (BSL, Mid, Post, and Follow Up) surrounding the training intervention. Study personnel performing the clinical assessments will be blinded to the intervention. We will first collect demographic information and a brief medical history including:

- Demographic variables: age, gender, date of birth (BSL only)
- Date of spinal cord injury, level of injury, and cause of injury (BSL only)
- Current and past medical history (BSL only)
- Current medications
- Current ambulatory ability in the home and community including any assistive devices used during ambulation

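### The HR reserve formula cancels to HR maximum, so the training zone as written lies 12–24 bpm below the reserve-based zone it names (assumed resting HR 60–80 bpm), close to the intended warm-up intensity

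*Combined protocol and SAP*

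**What the plan says.** The intensity rule is in section 5.1, Locomotor Training Interventions, under the Control group: "We will continuously adjust training parameters to maintain a target HR between 70 and 80% of estimated age-predicted HR reserve". The next lines define HR reserve as HR maximum minus HR resting, plus HR resting, and estimate HR maximum as 208 − 0.7 × age. The same term sets the 2.5-minute warm-up and cool-down: "Target heart rate during these periods will be between 50 and 65% of HR reserve". No other section gives a different formula or a target in beats per minute.

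The rule applies to both arms: "The locomotor training protocol described for the Control group will be used for the Experimental group with one exception", the exception being the movement amplification environment.

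Perceived exertion (RPE 15–17) is the second intensity control: "If target heart rate zones cannot be achieved during training, we will use RPE as a secondary measure of intensity". The Clinical Decision-Making rules then use the two measures together. Speed goes up if HR and RPE are below the zone and comes down under the condition "If HR and RPE are above the target zone". Where intensity and balance demands compete, "we will prioritize successful accomplishment of the task and stress progression of the dynamic balance demands", and the protocol accepts that lower functioning participants may fall short of the HR and RPE targets.

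**The concern.** The formula cannot do what its name says. Resting HR enters once with a minus sign and once with a plus sign, and no percentage stands between the two. It is therefore neither a reserve (which would stop at the subtraction) nor a target HR (which would multiply the reserve by the percentage before adding resting HR back).

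At stake is the delivered dose. Both arms are described as high intensity training, and the Control protocol is justified by evidence that higher intensity gave larger gains in walking speed than lower intensity. A zone set too low can hold participants below the effort the protocol names. It also leaves a reader, or a team repeating the trial, unable to tell whether 70–80% of reserve or 70–80% of maximum was delivered.

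**Working it through.** The plan states no target in bpm, so there is no figure of its own to reproduce. The check is algebra, followed by a range.

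Inputs:
- Training percentages 0.70 and 0.80; warm-up and cool-down percentages 0.50 and 0.65 (section 5.1).
- HRmax = 208 − 0.7 × age (section 5.1).
- Eligible ages 18 to 80 (section 5.4), so HRmax runs from 208 − 12.6 = 195.4 down to 208 − 56 = 152.0 bpm.
- Resting HR (R): not given. Assumed 60–80 bpm, with 50–90 bpm as a wider check.

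**Step 1, the cancellation.** (HRmax − R) + R = HRmax, exactly. The written limit at percentage p is p × HRmax.

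**Step 2, the reserve-based limit.** p × (HRmax − R) + R.

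**Step 3, the gap.** p × (HRmax − R) + R − p × HRmax = (1 − p) × R. It does not depend on age.

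| p | R = 60 | R = 70 | R = 80 |
|---|---|---|---|
| 0.70 | 18 | 21 | 24 |
| 0.80 | 12 | 14 | 16 |
| 0.50 | 30 | 35 | 40 |
| 0.65 | 21 | 24.5 | 28 |

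For the training zone the gap is thus 12–24 bpm over both limits. With R from 50 to 90 it would be 10–27 bpm.

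**Step 4, an example at age 50.** HRmax = 208 − 35 = 173, so the written training zone is 0.70 × 173 to 0.80 × 173 = 121.1–138.4 bpm.

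| R | Reserve-based training zone | Reserve-based warm-up zone | Written training zone as % of true reserve |
|---|---|---|---|
| 60 | 139.1–150.4 | 116.5–133.4 | 54–69% |
| 70 | 142.1–152.4 | 121.5–136.95 | 50–66% |
| 80 | 145.1–154.4 | 126.5–140.4 | 44–63% |

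The last column is (p × HRmax − R) / (HRmax − R). At R = 70 this is (121.1 − 70)/103 = 49.6% and (138.4 − 70)/103 = 66.4%. At this age the written and reserve-based training zones do not overlap for any of the three resting rates. The written training zone largely coincides with the reserve-based warm-up zone (50–65%).

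**Step 5, the eligible extremes, R = 60–80.** The written zone runs from 57–71% of true reserve (age 18, R = 60) to 37–58% (age 80, R = 80). It overlaps the 50–65% warm-up band at both ends.

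**Step 6, effect on the decision rule.** Take age 50, R = 70, HR 125 and RPE 13. Against the reserve-based zone, both measures are low and speed is raised. Against the written zone, HR is already within 121–138, so a rule that requires both to be low gives no increase.

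**The case against.** The strongest reply is that this is a drafting slip. The text names HR reserve in two places, and resting HR would be pointless in the formula unless a reserve-based target were meant. A licensed physical therapist directs all training, and the Time Line schedules a procedures manual and staff training. The working limits may well be right in practice. This stands as a limit on what can be inferred about the dose actually delivered. It does not correct the protocol, which nowhere says so.

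The warm-up comparison can also be challenged, because it sets the written training zone against the corrected warm-up zone. If the printed formula is used for both, warm-up at age 50 falls to 86.5–112.5 bpm and training stays above it. That is right. The comparison shows how far the written zone sits below the intended effort; it does not show that training and warm-up would coincide in a session. The near-exact match belongs to one assumed person, although the overlap persists across the eligible range.

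RPE 15–17 is a real safeguard. HR alone does not trigger slowing or rest, and the protocol reports that pilot participants were consistently brought into the HR and RPE zone. But RPE is named as secondary, for use when the HR zone cannot be reached; a zone set too low is easier to reach, and step 6 shows that it can block progression. What the pilot statement means also depends on which zone was used. Section 5.1 (Cardiovascular Risks) adds that spinal cord injury can alter the relation between HR and oxygen uptake, so a bpm gap does not convert simply into dose.

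Finally, the error is the same in both arms, and HR appears neither in the section 5.6 models nor among the outcomes. That stands too, and it limits the consequence to dose and reproducibility.

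**Conclusion.** The concern holds. The formula as printed equals HR maximum, and no other part of the protocol corrects it. The written training limits are 18–24 bpm too low at 70% and 12–16 bpm too low at 80% relative to the reserve-based zone the text names. The cancellation is certain; the bpm figures rest on the assumed resting HR of 60–80. Followed literally, both arms would be under-dosed on the HR criterion, with RPE as a partial check. There is no direct bias in the between-arm comparison, no effect on the sample size or primary outcomes, and no safety concern, since the printed limits ask for less exertion. It should be fixed because it is a wrong dosing rule in the operative description of the intervention.

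**What to change.** In section 5.1, replace the formula with: target HR = p × (HR maximum − HR resting) + HR resting. Use p = 0.70–0.80 for training and p = 0.50–0.65 for warm-up and cool-down, and apply these limits in the Clinical Decision-Making rules. Deleting the final resting HR term is not enough. It would define the reserve correctly, but 70–80% of that number read as a heart rate would be 0.70 × 103 to 0.80 × 103 = 72–82 bpm in the age 50, resting HR 70 example.

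If percentages of HR maximum are in fact intended, rename the quantity HR maximum in both places and drop resting HR.

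In either case, state which limits were used in any sessions already delivered. HR and RPE are recorded at every session, so the intensity achieved can be reported. The cost is one formula line and a check of the materials the therapists work from; no extra data are needed.
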